**Table 3: Schedule of Pharmacokinetic and Antidrug Antibody Assessments for Combination Therapy**

| Cycle                     | Day      | Scheduled time point                        | SRF617 PK sample a | Etrumadenant PK sample | Zimberelimab PK sample | SRF617 ADA sample a | Zimberelimab ADA sample |
|---------------------------|----------|---|-------------------------------|------------------------|------------------------|--------------------------------|-------------------------|
| 1                         | 1        | Predose b,c                      | X                             | X                      | X                      | X                              | X                       |
|                           |          | Immediately post SRF617 infusion (+ 30 min) | X                             |                        |                        |                                |                         |
|                           | 15 (± 1) | Predose b,c                      | X                             | X                      |                        |                                |                         |
|                           |          | Immediately post SRF617 infusion (+ 30 min) | X                             |                        |                        |                                |                         |
| 2                         | 1 (± 1)  | Predose b,c                      | X                             | X                      | X                      | X                              | X                       |
|                           |          | Immediately post SRF617 infusion (+ 30 min) | X                             |                        |                        |                                |                         |
|                           | 15 (± 1) | Predose c                        | X                             |                        |                        |                                |                         |
|                           |          | Immediately post SRF617 infusion (+ 30 min) | X                             |                        |                        |                                |                         |
| 3                         | 1 (± 1)  | Predose b,c                      | X                             | X                      | X                      | X                              |                         |
|                           |          | Immediately post SRF617 infusion (+ 30 min) | X                             |                        |                        |                                |                         |
|                           | 15 (± 1) | Predose b,c                      | X                             |                        |                        |                                |                         |
|                           |          | Immediately post SRF617 infusion (+ 30 min) | X                             |                        |                        |                                |                         |
| 4 and beyond d | 1 (± 1)  | Predose b,c                      | X                             | X                      | X                      | X                              | X                       |
|                           |          | Immediately post SRF617 infusion (+ 30 min) | X                             |                        |                        |                                |                         |
| EoT                       | --       | --  | X                             | X                      | X                      | X                              | X                       |

Abbreviations: ADA = antidrug antibody; EoT = end of treatment; PK = pharmacokinetics

a An additional blood sample for SRF617 PK and ADA should be drawn if a patient presents with a toxicity that meets the safety stopping rules, including such a toxicity outside of Cycle 1. See Section 4.6 and Section 6.1.12 for more details.

b On infusion visit days (Day 1 and Day 15 of each cycle), patients will hold etrumadenant administration until directed by trial personnel. Predose PK and ADA samples collected on these days should be collected before dosing of any study drugs. On all other days, patients may take etrumadenant at home.

c Pre-dose PK samples obtained on Cycle 1 Day 1 may be collected within 24 hours before SRF617 dosing. Predose PK samples obtained after Cycle 1 Day 1 may be collected within 2 hours before SRF617 dosing.

d Beginning with Cycle 4, SRF617 PK and ADA samples will be collected on Day 1 of each cycle and EoT. Etrumadenant and zimberelimab PK samples and zimberelimab ADA samples will only be collected on Cycle 4 Day 1, Cycle 8 Day 1, Cycle 13 Day 1, and EoT.

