|   | D1            | D2 | D8 ± 1 | D15 ± 1 | D1 ± 1  | D15 ± 1 | D1 ± 1        | D15 ± 1 |                               |                               |  |  |
| Zimberelimab administration n                  | X             |    |        |         | X   |         | X             |         |                               |                               |  |  |
| Etrumadenant administration n                  | X             | X  | X      | X       | X   | X       | X             | X       |                               |                               |  |  |
| Etrumadenant treatment compliance assessment n | X             |    |        | X       | X   | X       | X             |         | X                             |                               |  |  |
| Disease response assessments o                 |               |    |        |         | Response assessment every 12 wks (± 7 days) after C1D1 dosing |         |               |         | X                             |                               |  |  |

Abbreviations: ADA = antidrug antibody; AE = adverse event; aPTT = activated partial thromboplastin time; CXDX = Cycle X Day X; d = day; ECG = electrocardiogram; ECOG = Eastern Cooperative Oncology Group; EoT = end of treatment; FT4 = free thyroxine; ICF = informed consent form; INR = international normalized ratio; LDH = lactate dehydrogenase; LFT = liver function test; PBMC = peripheral blood mononuclear cell; PK = pharmacokinetic(s); PAP = prostatic acid phosphatase; PSA = prostate-specific antigen; PT = prothrombin time; SAE = serious adverse event; TSH = thyroid stimulating hormone

a The EoT visit should occur for any patient when they discontinue the last study drug. Each assessment need not be performed if the patient had an identical assessment within the previous 2 weeks. Disease response assessment is not required for patients whose most recent scan was ≤ 6 weeks before EoT visit.

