#### **3.2. Secondary Endpoints**

- ORR per PCWG3 criteria, ORR per RECIST v1.1, duration of response, disease control rate (DCR), PSA50 response, PSA decline  $\geq 30\%$  (PSA30) response, time to PSA progression, radiographic PFS, and landmark PFS rate at 6 and 12 months
- Serum concentrations of SRF617
- Percentage of patients with ADAs to SRF617
- Incidence of SSEs

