#### 4.4. Dosing Frequency

SRF617 will be administered in combination with etrumadenant and zimberelimab in 28-day cycles according to the following dosing schedule:

- SRF617 1400 mg IV q2 weeks on Days 1 and 15
- Etrumadenant 150 mg orally daily
- Zimberelimab 480 mg IV q4 weeks on Day 1

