## 4.7. Treatment Discontinuation

A patient should be discontinued from a study drug if, in the opinion of the Investigator or Sponsor, it is medically necessary or if it is the wish of the patient. Discontinuation of study treatment does not represent withdrawal from the trial.

All patients should undergo the Safety Follow-up visit when they discontinue the last study drug (Section 6.4).

Patients will be discontinued from all study drugs for any of the following reasons:

- AE(s) that requires permanent discontinuation of all study drugs
- Disease progression as measured by the appropriate response criteria
  - Note: Patients who meet criteria may continue past disease progression (see Section 6.3)
- Noncompliance with protocol
- Investigator decision (specific justification to be documented)
- Patient is lost to follow-up
- Termination of the trial by the Sponsor
- Voluntary withdrawal by patient

AEs leading to the discontinuation of study drug will be followed until resolution to Baseline or until the event is considered stable or chronic. Patients who discontinue treatment with any study drug for any reason, but who are deriving clinical benefit (objective response or stable disease) from one or both of the remaining drugs, may continue to receive those study drugs at the discretion of the Investigator and Sponsor.

The End of Treatment (EoT) visit should occur within 7 days after a patient discontinues the last study drug. Disease response assessment is not required for patients whose most recent scan was  $\leq 6$  weeks before the EoT visit. Other assessments previously performed within the previous 2 weeks need not be repeated at EoT. For patients who discontinue the last study drug because of a treatment interruption lasting  $> 56$  days, the EoT visit should be completed as soon as possible.

All patients will have a Safety Follow-up visit at 30 days after the last dose of SRF617, 30 days after the last dose of etrumadenant, or 90 (+ 7) days after the last dose of zimberelimab (30 days after the last dose of zimberelimab if the patient initiates new anticancer therapy), whichever is later. If possible, this visit should occur before the initiation of any subsequent anticancer therapy. At a minimum, this visit should include collection of AEs and concomitant medications/procedures.

Response assessments will be conducted per Table 2 until the patient experiences progressive disease or discontinues the trial.

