### **6.2.2. Antidrug Antibody Assay**

An ADA assay will be performed at a central laboratory for SRF617 immunogenicity testing. Refer to the Laboratory Manual for sample handling procedures and shipping requirements. ADA assays will also be performed for zimberelimab, with sparse sampling throughout the trial. The time points for the collection of this assessment are detailed in [Table 3](#). An additional ADA sample, beyond those listed, may be requested (when feasible) at the time of any unusual safety event, ie, an AE different in type and severity from that which is expected in the setting of SRF617, etrumadenant, or zimberelimab use. Patients who test positive for SRF617 ADA will be tested until their ADA levels revert to Baseline or the end of the trial.

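### The two-week End of Treatment waiver does not exempt the SRF617 ADA sample, so a patient who stops early in Cycle 1 can have no post-exposure ADA result

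*Protocol*

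**What the plan says.** The secondary endpoint (protocol Section 3.2) is "Percentage of patients with ADAs to SRF617". No denominator is attached to it.

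Table 3 places SRF617 ADA samples at the predose time on Day 1 of Cycles 1, 2 and 3. After that, "Beginning with Cycle 4, SRF617 PK and ADA samples will be collected on Day 1 of each cycle and EoT". The Day 15 rows have PK samples but no ADA sample, and the table has no Safety Follow-up row. Footnote b fixes the order on infusion days: "Predose PK and ADA samples collected on these days should be collected before dosing of any study drugs".

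The EoT visit is due within 7 days of stopping the last study drug. Table 2 footnote a says of that visit: "Each assessment need not be performed if the patient had an identical assessment within the previous 2 weeks". Section 4.7 repeats the allowance without requiring that the assessments be identical: "Other assessments previously performed within the previous 2 weeks need not be repeated at EoT". Imaging has its own 6-week rule. ADA has no separate rule.

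Two other provisions bear on the point. Table 3 footnote a: "An additional blood sample for SRF617 PK and ADA should be drawn if a patient presents with a toxicity" of the kind that meets the stopping rules, in Cycle 1 or later. Section 6.2.2: "Patients who test positive for SRF617 ADA will be tested until their ADA levels revert to Baseline or the end of the trial".

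**The concern.** The EoT draw is the only scheduled ADA sample that does not precede a dose. For a patient who stops in Cycle 1 it is also the only one that follows any exposure to SRF617. A general rule meant to avoid duplicate tests can cancel it on the strength of a baseline sample, which cannot show treatment-emergent ADA.

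Section 6.2.2 also requires patients with a positive result to be retested, possibly to the end of the trial, but no visit after EoT carries an ADA draw. The Safety Follow-up visit may be a telephone call (Table 2 footnote b).

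What is at stake is the completeness of a named secondary endpoint in a trial with 15 treated patients (SAP Section 2), where one result moves the percentage visibly.

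**Working it through.** The documents give no ADA rate, ADA precision or count of early stoppers, so there is no stated figure to reproduce. The check is day arithmetic on the schedule, then simple proportions.

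**Inputs.** Baseline ADA draw on Day 1 (Table 3). Waiver window 14 days (Table 2 footnote a, Section 4.7). EoT 0 to 7 days after stopping (Section 4.7). Dosing: "SRF617 1400 mg IV q2 weeks on Days 1 and 15" (Section 4.4). Treated patients 15 (SAP Section 2); planned patients 40 (protocol Section 9.1).

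**1. When the waiver leaves only the baseline.** EoT ADA may be skipped if EoT day − 1 ≤ 14, that is, if EoT falls by Day 15.
- Stop by Day 8: the latest EoT is 8 + 7 = Day 15, always inside the window.
- Stop on Days 9 to 15: inside only if EoT is held by Day 15.
- Stop on Day 16 or later in Cycle 1: EoT is at least 15 days after baseline, so the sample is required.

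**2. Patients who reach Cycle 2 Day 1 (about Day 29).** That predose draw follows the Day 1 and Day 15 infusions, so it is a post-exposure sample. The same holds for every later Day 1. If EoT ADA is waived for these patients, what is lost is ADA that emerges between the last Day 1 draw and EoT, an interval of at most 14 days.

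**3. What the triggered sample covers.** The criteria in Section 4.6 include treatment-related toxicity that ends treatment during Cycle 1. Those patients should have an extra ADA sample under Table 3 footnote a. Patients who stop in the first two weeks for progression, by their own choice or by investigator decision (Section 4.7) have no such trigger.

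**4. Size.** With all n treated patients as the denominator, each missed positive costs 1/n:
- n = 15: 1/15 = 6.7 percentage points.
- n = 40: 1/40 = 2.5 percentage points.

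That is the loss when an unsampled patient would in fact have been positive. Suppose instead that k unsampled patients carry the same ADA risk as the rest and count as not positive. The observed rate is then the true rate × (n − k)/n. The value of k is an assumption, because the documents give none. For a true rate of 10%:

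| k | n = 15 | n = 40 |
|---|---|---|
| 1 | 10 × 14/15 = 9.33% | 10 × 39/40 = 9.75% |
| 2 | 10 × 13/15 = 8.67% | 10 × 38/40 = 9.50% |
| 3 | 10 × 12/15 = 8.00% | 10 × 37/40 = 9.25% |

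If the denominator is patients with at least one post-dose sample, the k patients drop out of both counts and this counting bias is zero. That denominator does not recover the late-emerging ADA in step 2, whose size cannot be computed from the documents.

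**5. Which denominator applies.** Section 2.2 lists ADA among the additional safety parameters. Section 9.6 uses the Safety Analysis Set for all safety endpoints, and Section 9.2.2 defines that set as everyone given any study drug. The protocol defines no ADA-evaluable set. SAP Section 1.1 removes the Immunogenicity Analysis Set, and SAP Section 12.3 leaves the analysis to a separate report. All treated patients is therefore the protocol's default, but it is not an explicit rule for this endpoint.

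**The case against.** The strongest reply is that the gap is narrow and partly covered. Predose is not pre-exposure: only the Cycle 1 Day 1 sample is a true baseline, so the waiver removes all post-exposure information only for stops in roughly the first two weeks. Patients who stop in Cycle 1 for related toxicity, in whom ADA is arguably of most interest, already trigger an extra sample. EoT is tied to stopping the last study drug, so stopping SRF617 alone need not bring an early EoT. Section 6.2.2 also allows optional samples for unusual safety events.

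All of this stands, and it limits the point. It does not close the gap. The triggered sample does not reach stops without a qualifying toxicity. It is drawn at presentation, which may be the infusion day itself. The optional samples are only requested when feasible.

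A reader might go further and infer four things that the documents do not support.
- *That the ADA percentage is biased low.* This holds only if all treated patients form the denominator and unsampled ones count as not positive. The plan never states the second condition.
- *That a large share of patients lose their ADA result.* EoT may often fall within two weeks of some Day 1, but after Cycle 2 Day 1 a post-exposure sample is already in hand.
- *That persistence of ADA cannot be assessed.* Section 6.2.2 requires retesting of positives. What is missing is a scheduled visit at which to do it.
- *That EoT PK needs the same exemption because earlier samples were predose.* Table 3 has post-infusion SRF617 PK samples on Days 1 and 15 of Cycles 1 to 3 and on Day 1 afterwards.

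**Conclusion.** The gap is real and limited. As written, a patient who stops all study drugs by Day 8 of Cycle 1, or on Days 9 to 15 with EoT by Day 15, can finish with no post-exposure SRF617 ADA sample unless a stopping-rule toxicity prompts one. For patients who reach Cycle 2 Day 1, the waiver can lose only ADA that emerges after the last Day 1 draw.

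The number affected is unknown. Over the Safety Analysis Set, each missed positive costs 6.7 points at 15 patients and 2.5 points at 40. Over patients with a post-dose sample, the counting bias from unsampled patients is zero. The day limits assume that the baseline draw is on Day 1 and that sites use the waiver as written.

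The retesting instruction in Section 6.2.2 needs a named visit before it can be carried out. This is a cheap improvement to a secondary endpoint. It does not put the trial's main conclusions in doubt.

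**What to change.** 1. Add a footnote to Table 3, with a matching phrase in Table 2 footnote a and Section 4.7: the two-week waiver does not apply to the EoT SRF617 ADA sample, at minimum when the patient has no post-dose ADA sample.
2. Add a Safety Follow-up row to Table 3 for SRF617 ADA, limited to patients whose last ADA result was positive or who have no post-dose sample. This gives Section 6.2.2 a visit. It also helps the earliest stoppers, because the documents do not say how soon ADA would be expected to appear and an EoT sample in the first two weeks may be early.
3. In the separate immunogenicity report, give the ADA percentage over patients with at least one post-dose ADA sample, and state how many treated patients had none.

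The cost is one extra tube, and a few telephone follow-ups become clinic visits. Enrollment has closed, so items 1 and 2 can help only patients who have not yet passed those visits. Item 3 needs no new data and can still be adopted in full.

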## LIST OF ABBREVIATIONS AND DEFINITIONS OF TERMS

| Abbreviation | Definition                                       |
|--------------|--|
| ADA          | antidrug antibody                                |
| ADL          | activities of daily living                       |
| ADP          | adenosine diphosphate                            |
| AE           | adverse event                                    |
| AESI         | adverse event of special interest                |
| ALT          | alanine aminotransferase                         |
| AMP          | adenosine monophosphate                          |
| ANC          | absolute neutrophil count                        |
| aPTT         | activated partial thromboplastin time            |
| ARSI         | androgen receptor signaling inhibitor            |
| AST          | aspartate aminotransferase                       |
| ATP          | adenosine triphosphate                           |
| BCRP         | breast cancer resistance protein                 |
| C1D1         | Cycle 1 Day 1                                    |
| CNS          | central nervous system                           |
| CR           | complete response                                |
| CTLA-4       | cytotoxic T-lymphocyte-associated protein 4      |
| DCR          | disease control rate                             |
| DoR          | duration of response                             |
| DVT          | deep vein thrombosis                             |
| ECG          | electrocardiogram                                |
| ECOG         | Eastern Cooperative Oncology Group               |
| eCRF         | electronic case report form                      |
| EDC          | electronic data capture                          |
| ENTPD1       | ectonucleoside triphosphate diphosphohydrolase-1 |
| EoT          | end of treatment                                 |
| FSH          | follicle-stimulating hormone                     |
| GCP          | Good Clinical Practice                           |
| GI           | gastrointestinal                                 |
| GLP          | Good Laboratory Practice                         |
| HBcAb        | hepatitis B core antibody                        |

|           |  |
|-----------|--|
| HBsAg     | hepatitis B surface antigen  |
| HBV       | hepatitis B virus  |
| HCV       | hepatitis C virus  |
| HCV Ab    | hepatitis C virus antibody   |
| HR        | hazard ratio   |
| HSPC      | hormone-sensitive prostate cancer  |
| ICF       | informed consent form  |
| ICH       | International Conference on Harmonisation                                |
| IEC       | independent ethics committee   |
| IFN       | interferon   |
| IgG4      | immunoglobulin G4  |
| IL        | interleukin  |
| INR       | international normalized ratio   |
| IRB       | institutional review board   |
| IV        | intravenous(ly)  |
| KO        | knockout   |
| LDH       | lactate dehydrogenase  |
| mCRPC     | metastatic castration-resistant prostate cancer                          |
| MedDRA    | Medical Dictionary for Regulatory Activities                             |
| NCI-CTCAE | National Cancer Institute Common Terminology Criteria for Adverse Events |
| NECA      | 5'-N-ethylcarboxamide adenosine  |
| NK        | natural killer   |
| ORR       | objective response rate  |
| OS        | overall survival   |
| PAP       | prostatic acid phosphatase   |
| PBMC      | peripheral blood mononuclear cell  |
| pCREB     | cAMP response element-binding protein                                    |
| PCWG3     | Prostate Cancer Working Group 3  |
| PD-1      | programmed death receptor-1  |
| PD-L1/2   | programmed death-ligand 1/2  |
| PFS       | progression free survival  |
| PK        | pharmacokinetic(s)   |

|                   |  |
|-------------------|--|
| PR                | partial response/remission                     |
| PSA               | prostate-specific antigen                      |
| PSA 30 | PSA decline $\geq$ 30%                         |
| PSA 50 | PSA decline $\geq$ 50%                         |
| PT                | prothrombin time                               |
| q2 weeks          | once every 2 weeks                             |
| q4 weeks          | once every 4 weeks                             |
| QTc               | heart rate-corrected QT interval               |
| QTcF              | QT interval corrected with Fridericia's method |
| RBC               | red blood cell                                 |
| RECIST            | Response Evaluation Criteria in Solid Tumors   |
| RP2D              | recommended Phase 2 dose                       |
| SAE               | serious adverse event                          |
| SAP               | statistical analysis plan                      |
| SRC               | Safety Review Committee                        |
| SSE               | symptomatic skeletal events                    |
| TEAE              | treatment-emergent adverse event               |
| TME               | tumor microenvironment                         |
| TNF $\alpha$      | tumor necrosis factor alpha                    |
| ULN               | upper limit of normal                          |

